2.3. For retrospective research studies, provide the “look-back” period. (e.g., December 1, 1999 through December 31, 2008.)

[figure not shown]
3. Study Duration

3.1. Provide the estimated length of time to enroll all subjects and complete the study.

We want to enroll a total of 492 poorly controlled diabetic veterans and 206 mentors with currently good glucose control. In stage 1 there will be 206 poorly controlled diabetics in the peer mentoring arm and 206 mentors. Mentors who withdraw from the study will be replaced by additional mentors to ensure that all 206 poorly controlled diabetics in the peer-mentoring arm have mentors. In stage two there will be 144 mentors (former mentees) of which 72 will be randomized to being a mentor and 72 will be randomized to usual care. In addition, there will be 128 poor controlled diabetics 56 of whom will be in usual care and 72 of whom will be randomized to receiving peer mentoring from FFM. We project being able to enroll 7-8 new poorly controlled diabetics per week with two research assistants. Even considering the staggered start times, we anticipate it will take 14-16 months to complete enrollment and another 18-24 months to complete follow-up for a total of 38-40 months. After that we anticipate it will take an additional 1-2 months to complete the analysis. See sample size section for further description of required sample.

3.2. Explain the expected duration of subject participation including any follow-up.

The active time for each participant in the study will be roughly 18-24 months depending on which arm they are randomized to. 12-18 months of face-to face visits with an additional 6 months after the last in-person visit where each participant’s electronic medical record (EMR) will be under electronic review. Figure 2 depicts the flow of participants through the study.

Figure 2: Flow of Participants Through Study

3.3. Specify the projected date of completion of the proposed study.

Enrollment started September 27, 2012 and we anticipate completion of the study by December 31, 2015

4. **Drug Information** (If not applicable state, "Not Applicable.") **N/A**

- 4.1. Specify if the drug or biological agent is:
 - 4.1.1. FDA approved
 - 4.1.2. Used for off-label purposes
 - 4.1.3. Not yet FDA approved.
- 4.2. Include the FDA Investigational New Drug (IND) number for all non-FDA approved and off-label drugs, biological agents or nutritional supplements. If not applicable state, "Not Applicable."

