In order to assure 72 in each arm for stage 2, we will need a total of 144 mentees in stage 1. Again, to protect against possible attrition, we inflate that by 16% and enroll 171 mentees in stage 1. A corresponding number of mentors (171) will be recruited for stage 1. There will be no randomization of mentors in stage 1. Since usual care for stage 1 can be combined with usual care for stage 2, there is no need for a 1:1 randomization. Initially, a 1:1 randomization was used, but after evaluation we believe we can switch to a 2:1 randomization to avoid recruiting more usual care patients than necessary. With this change we will enroll approximately 139 patients to usual care in stage 1.

The combined number of poorly controlled diabetic patients receiving usual care will be approximately 195. The number of poorly controlled diabetic patients receiving peer mentoring will be 232 (171 in stage 1 and 72 in stage 2). The number of mentors in stage 1 will be 171, and the number of mentors in stage 2 will be 72 (from among those who received mentoring in stage 1). The total number of patients in the study will be 594.

A recent analysis of clinical data from the CMC VAMC and its surrounding CBOCs indicate that in the last year there were 1,248 patients who would have qualified to be mentees and 1,810 who would have qualified to be mentors.

4.2. Define plans for data and statistical analysis, including key elements of the statistical plan, stopping rules and endpoints.

For Stage 1: We will test these primary hypotheses using an unadjusted intent-to-treat analyses, i.e., with adjustment for only baseline HbA_{1c}. The primary tests will assess the significance of the coefficients associated with the treatment assignment in a longitudinal linear model of the repeated HbA_{1c} as a function of treatment, where the active group (peer mentoring) is compared to the control group via an indicator variable. Standard t-tests will determine whether a significant difference in HbA_{1c} improvement occurred between the treatment arm compared to the control arm. To account for the fact that we are doing multiple tests, we will use the Bonferroni method and consider a treatment to be significantly different than the control if the p-value is less than $0.05/2=0.025$.

| Stage 2 Analysis:

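### The sample size section's totals of 232 and 594 do not follow from its own parts (243 and 609), and its stage 1 numbers conflict with the enrolment target of 492 and 206

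*Combined protocol and SAP*

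**What the plan says.** The plan states its size in two places that matter here.

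**Section U.4.1 (power calculations)** is the only derivation. It takes 64 per arm, raises this to 72 for 10% attrition, and so needs 144 former mentees for re-randomisation. For stage 1 it then says: "Again, to protect against possible attrition, we inflate that by 16% and enroll 171 mentees in stage 1". On mentors: "A corresponding number of mentors (171) will be recruited for stage 1". On controls: "With this change we will enroll approximately 139 patients to usual care in stage 1". With about 56 more in stage 2: "The combined number of poorly controlled diabetic patients receiving usual care will be approximately 195". Its two summary totals are "The number of poorly controlled diabetic patients receiving peer mentoring will be 232 (171 in stage 1 and 72 in stage 2" and "The total number of patients in the study will be 594". It also says that the 72 stage 2 mentors come from the stage 1 mentees, so they add nobody.

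**Section K.3.1 (study duration)** sets the enrolment target: "We want to enroll a total of 492 poorly controlled diabetic veterans and 206 mentors with currently good glucose control". For stage 1: "In stage 1 there will be 206 poorly controlled diabetics in the peer mentoring arm and 206 mentors". Replacements for mentors who withdraw come on top. Stage 2 has 128 new patients, 56 in usual care and 72 mentored by former mentees. The reader is sent to the sample size section for detail. Sections M.2.3.1.1 (charts to be accessed) and P.1.1 (planned enrolment) repeat 492 and 206.

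**The concern.** A sum printed next to its own two parts is wrong, and the study total cannot be rebuilt from the groups listed beside it. Separately, the only derivation arrives at 171 stage 1 mentees, while three other sections recruit to a target built on 206. The target therefore has no derivation, and the derivation does not lead to the target.

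This bears on more than bookkeeping. The stage 1 mentees are the pool that must yield 144 people for the second randomisation, after loss to follow-up and after removal of those judged unsuitable as mentors (section M.1.1). Whether that pool was sized for 16% or for roughly 30% shrinkage decides how much margin hypothesis H3 (becoming a mentor versus not) has.

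**Working it through.** **1. Reproduce the upstream figures (U.4.1).** Difference 0.8, SD 1.6, so standardised difference 0.8/1.6 = 0.5. U.4.1 states no alpha; I take two-sided 0.05, as given for the H2 test in U.4.2. The two-sample t-test needs 63.8, i.e. 64 per arm, with power 80.1% at 64. Then 64/0.90 = 71.1, i.e. 72; 2 × 72 = 144; 144/0.84 = 171.4, printed as 171. These all agree with the plan. (Read literally, raising 144 by 16% is 144 × 1.16 = 167.0, so 171 fits only as division by 0.84.)

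**2. Summary totals in U.4.1.**

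- Usual care: 139 + 56 = 195. Agrees.
- Mentored: 171 + 72 = 243. Printed 232, which is 11 too low.
- All patients: 195 + 243 + 171 = 609. Printed 594, which is 15 too low.
- Other readings of 594: keeping 232 gives 195 + 232 + 171 = 598; leaving out stage 1 mentors gives 438 (427 with 232); counting the 72 stage 2 mentors again gives 681. None gives 594.

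**3. U.4.1 against K.3.1, M.2.3.1.1 and P.1.1.**

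| | U.4.1 | K.3.1 and the other two | Difference |
|---|---|---|---|
| Stage 1 mentees | 171 | 206 (K.3.1) | 35 |
| Stage 1 mentors | 171 | 206 | 35 |
| Stage 1 usual care | about 139 | 158 (residual, not printed) | about 19 |
| Stage 2 mentored + usual care | 72 + 56 | 72 + 56 (K.3.1) | 0 |
| Poorly controlled patients | 438 | 492 | 54 |
| All, before replacement mentors | 609 | 698 | 89 |

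Here 158 = 492 − 206 − 128, 438 = 171 + 139 + 72 + 56, and 698 = 492 + 206. Stage 2 is identical in both sets, so the whole gap lies in stage 1.

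**4. Implied shrinkage before re-randomisation.** 1 − 144/171 = 15.8%, in line with the stated 16%. 1 − 144/206 = 30.1%, stated nowhere.

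**5. What the choice means for H3.** Per-arm number at analysis = pool × (1 − earlier loss)/2 × 0.90.

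- At the plan's own rates: 171 × 0.84/2 × 0.90 = 64.6, power 80.5%.
- Largest earlier loss that still leaves 64 per arm: 1 − (128/0.90)/171 = 16.8% from 171, and 1 − (128/0.90)/206 = 31.0% from 206.
- Larger earlier losses, as assumptions only (the documents give no such rates): from 171, losses of 20%, 25% and 30% leave 61.6, 57.7 and 53.9 per arm, with power 78.6%, 75.9% and 72.9%. A 30% loss from 206 leaves 64.9 and 80.7%.

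**The case against.** The strongest reply is that nothing which sizes or tests a hypothesis is wrong. The 64, 72 and 144 reproduce, stage 2 agrees throughout, and 232 and 594 feed no later calculation. That is true, and the H3 powers below 80% come from assumed losses, not planned ones. But the planned sample size is itself a figure that the trial relies on, and the documents give no single value for it.

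Second, section M.1.1 says that stage 1 was over-enrolled for loss to follow-up and for removal of unsuitable mentors, which could explain a pool larger than attrition alone requires. This is a reason without a number. The only stated allowance is 16%, and it gives 171.

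Third, three sections agree on 492 and 206, and the sets are roughly compatible with an enlargement: 35 extra mentees at 2:1 add about 17.5 controls, and 139 + 17.5 = 156.5 is close to 158. Perhaps U.4.1 was simply not updated. Likewise, 594 equals 195 + 232 + 167, and 232 equals 144/0.90 + 72, so both may be leftovers. These are inferences; the text marks neither set as superseded, so the team must say.

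Replacement mentors do not explain 206, because K.3.1 and P.1.1 list them as additional and K.3.1 also gives 206 mentees. Rounding does not explain 232 or 594: only the usual care counts are described as approximate, and 139 + 56 is exactly 195. Figures 1 and 2 are not in the text supplied and may carry counts, but they could not reconcile sentences that print different numbers.

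**Conclusion.** Wrong as written. In U.4.1, 232 should be 243 and 594 should be 609 on its own parts. Its stage 1 plan also contradicts the enrolment target in K.3.1, M.2.3.1.1 and P.1.1 by 35 mentees, 35 mentors and, by subtraction, about 19 usual care patients: 438 against 492 poorly controlled, and 609 against 698 in all, both before replacement mentors. These are sums of printed figures and need no assumption beyond the residual of 158.

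Stated power stands at the plan's own 16% and 10% loss rates. What changes between the sets is the tolerance for loss or removal before re-randomisation, 16.8% against 31.0%, given the later 10% loss and the two-sided 0.05 t-test. The correction is needed because the number to enrol and the allowance behind it are both undefined.

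**What to change.** 1. The study team confirms which stage 1 set is current and uses it in U.4.1, K.3.1, M.2.3.1.1 and P.1.1. The documents do not settle this.
   - *If 171 is current:* U.4.1 reads 243 mentored, 195 usual care, 171 stage 1 mentors, total 609. In the other three sections 438 and 171 replace 492 and 206, and K.3.1 gives 171 stage 1 mentees.
   - *If 206 is current:* U.4.1 reads 278 mentored (206 + 72), 214 usual care (158 + 56), 206 stage 1 mentors, total 698. The allowance that leads from 144 to 206 is stated in place of 16%.
   - *In both cases:* note that replacement mentors are additional to the total.
2. In U.4.1, the stage 2 sentence that places the 72 patients to be mentored in usual care should place them in the arm mentored by former mentees. Its own parenthesis and K.3.1 show that this is a wording slip.
3. The 64, 72, 144 and 80% power statements stay as they are.

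The cost is a text correction by protocol modification, with no change to any test. Whether recruitment changes depends on the set that staff already use: moving from 171/438 to 206/492 means 54 more poorly controlled patients and 35 more mentors; if they already work to 206/492 and that set is confirmed, nothing changes.

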2.1.3. Protocol modifications

If we desire to modify the protocol we will submit a modification to the IRB and not act on the modification until it has been approved.

3. **If applicable, define the plan for subjects if research shows results such as:**
 - 3.1. Depression **We will only use a depression screening tool and not assessing for depression. If the participant is willing and they screen positive for depression we will notify the participant's primary care provider.**
 - 3.2. Suicide **Will not be assessed**
 - 3.3. Abuse **Will not be assessed**
4. **Statistical Analysis**
 - 4.1. Include statistical power calculations and the assumptions made in making these calculations.

We will randomize 72 mentees from stage 1 to each arm of stage 2. To achieve 80% power to detect a 0.8 unit change in HbA1c, with standard deviation of 1.6, a sample of 64 patients per arm would be required. But to protect against possible attrition, we will inflate that by 10% and enroll 72 participants into each arm. Literature and guidelines suggest that an average decrease of 1 unit in HbA1c would provide a clinically meaningful improvement in health. We chose a 0.8 unit change to be conservative. We base our standard deviation of 1.6 on our pilot study and other studies of low control DM populations.

For stage 2 we will also randomize poorly controlled diabetics into mentoring or usual care arms. We will need 72 in the usual care arm (to be mentored by the 72 stage 1 mentees who become mentors). Since usual care for stage 2 can be combined with usual care for stage 1, there is no need for a 1:1 randomization. Initially, a 1:1 randomization was used, but after evaluation we

believe we can now switch to a 2:1 randomization to avoid recruiting more usual care patients than necessary. With this change we will enroll approximately 56 patients to usual care in stage 2.

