H2. Compared to usual care, veterans who receive peer mentoring from former mentees will have improved glucose control as measured by HbA_{1c}, BP, LDL levels, DM quality of life, and depression scores: We will examine the effectiveness of the intervention at 6 months and further examine sustainability at 12 and 18 months. 18 month assessments will only be of HbA_{1c}, BP, and LDL levels as derived from the EMR. We will test these primary hypotheses using an intent-to-treat (ITT) analyses, i.e., including all patients who completed a baseline assessment, as randomized. We will use linear and random effects longitudinal models to perform the ITT comparisons at each of the follow-up visits. Our primary outcomes will be HbA_{1c}, BP, LDL levels, DM quality of life, and depression scores. Our models will include a random effect for patient. The models will include the following fixed effects: a main effect for follow-up visit (with baseline visit as the reference), intervention group, and their interactions. Tests of the interaction terms will be used to determine the ITT difference between groups with respect to change from baseline. To examine whether veterans who received peer mentoring from former mentees have improved glucose control, BP, LDL levels, DM quality of life, and depression scores compared to veterans in the usual care group at 6 months, compared to baseline, we will implement these random effects models with mentee HbA_{1c}, BP, LDL, DM quality of life score, or depression score as the dependent variable. The ITT test for effectiveness will be based on HbA_{1c} and will be two-sided, with

$\alpha=0.05$ and will be based on the magnitude and statistical significance of the time*intervention interaction term at 6 months. To examine sustainability of improvement in glucose control, BP, LDL levels, DM quality of life, and depression scores we will use the same test, but will examine the intervention group*12 month time interaction term. To examine sustainability of improvement in glucose control, BP, and LDL levels at 18 months we will again use the same test, but will examine the intervention group*18 month interaction term.

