We will check model fit by inspecting residual plots, and will assess improvement in fit with different correlation structures for the random effects. While we do not anticipate confounding in our ITT estimates because of the stratified and blocked randomization of patients, confounding due to imbalance in patient characteristics may still occur by chance. Tests for evidence of confounding will be performed by comparing baseline characteristics, between control and intervention group. Confounders will be identified as variables that are significant at the 0.20 level and we will include these as adjustment variables (fixed effects) in our analyses. These multivariable models will reduce the impact of potential bias due to confounding, as well as improve the statistical power by reducing the amount of unexplained variation in the outcome variable.

Extensive efforts will be made to collect complete information on each participant enrolled in the study. While we do not expect to be confronted with nonignorable missing data, we will nevertheless assess the sensitivity of treatment effect estimates to missing outcome data in a number of ways. We will compare the number of visits completed by participants in each arm as an additional secondary outcome, using the chi-square test. We will also compare observed characteristics of subjects with complete follow-up to those with missing data and will attempt to ascertain the reasons for missing data in subjects with incomplete follow-up.

H3: Compared to past mentees who are not randomized to becoming a mentor, past mentees randomized to becoming a mentor will have better glucose control, BP, LDL levels, DM quality of life, and depression scores: To examine whether past mentees who become mentors have better glucose control, BP, LDL levels, DM quality of life, and depression scores than past mentees who do not become mentors, the dependent variable in this analysis will be past mentee HbA_{1c}, BP, LDL level, DM quality of life score, and depression score and the intervention group will be the randomization group for former mentees. As we described above, tests of the interaction terms for each follow-up time (i.e. 6, 12 months, and 18 months) with intervention group will be used to determine the ITT difference between groups with respect to change from baseline HbA_{1c}, BP, LDL level, at each follow-up time and DM quality of life score, and depression score at 6 and 12 months.

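### H2 and H3 test change from baseline although Stage 1 adjusts for baseline, and covariates screened at p<0.20, if entered as main effects, add almost nothing to that test

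*Combined protocol and SAP*

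**What the plan says.** All references are to section U.4 of the combined protocol and SAP unless noted.

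- **Stage 1 (4.2).** The primary analysis is "an unadjusted intent-to-treat analyses, i.e., with adjustment for only baseline" HbA1c, and the test is on the treatment coefficient.
- **H2 (4.2, Stage 2 Analysis).** A model with a random patient effect has as fixed effects "a main effect for follow-up visit (with baseline visit as the reference), intervention group, and their interactions". Baseline is therefore one of the responses, and the arms are free to differ there. "Tests of the interaction terms will be used to determine the ITT difference between groups with respect to change from baseline". The effectiveness test is the 6-month interaction for HbA1c, two-sided at 0.05. The ITT set is everyone with a completed baseline assessment.
- **H3 (4.2).** It takes over the same interaction tests by reference to the H2 description.
- **Covariates (4.2).** Baseline characteristics are compared between arms. "Confounders will be identified as variables that are significant at the 0.20 level and we will include these as adjustment variables (fixed effects"). Two benefits are claimed. One is protection against chance imbalance: "These multivariable models will reduce the impact of potential bias due to confounding". The other is a gain in precision, since the same adjustment is expected to act on residual variance "as well as improve the statistical power by reducing the amount of unexplained variation in the outcome variable".
- **Sample size (4.1).** "To achieve 80% power to detect a 0.8 unit change in HbA1c, with standard deviation of 1.6, a sample of 64 patients per arm" is required, raised to 72 for attrition. Usual care from both stages may be combined: "The combined number of poorly controlled diabetic patients receiving usual care will be approximately 195", of whom about 56 come from stage 2.

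**The concern.** The same outcome, collected in the same way, is analysed differently in the two stages, and no reason is given. Leaving the baseline difference between arms free discards the information that randomised arms have the same expected baseline, so H2 and H3 may give up precision that the baseline draw already offers.

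The covariate rule is the plan's stated remedy for chance imbalance and its stated source of extra power. If it does neither for the test that decides H2 and H3, the text describes a protection that is not there. The covariate set also stays unknown until the arms have been compared.

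**Working it through.** **1. The plan's own figure.** Inputs from 4.1 and 4.2: difference 0.8, SD 1.6, two-sided alpha 0.05, 80% power. An unadjusted two-sample t-test has power 0.795 at 63 per arm and 0.801 at 64, so 64 reproduces. 64/(1−0.10) = 71.1, which rounds up to 72. The stated numbers are correct for an unadjusted test. The text does not say whether 1.6 is the SD of HbA1c or of its change.

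**2. Change score against baseline adjustment.** Let r be the correlation of baseline with follow-up, k the baseline SD divided by the follow-up SD, and σ the follow-up SD.

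- Variance of change: σ²(1 + k² − 2rk)
- Residual variance after baseline adjustment: σ²(1 − r²)
- Saving: 1 − (1 − r²)/(1 + k² − 2rk)

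Since (1 + k² − 2rk) − (1 − r²) = (k − r)², the saving is never negative and is zero when r = k. Neither r nor k is in the documents. The entry rule (HbA1c above 8%) may make k less than 1. The analysed baseline, however, is a separate draw at enrolment (M.1.1, Patients and Settings), so k is shown as a range.

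| Variance saving | r=0.3 | r=0.5 | r=0.7 |
|---|---|---|---|
| k=1 | 35% | 25% | 15% |
| k=0.9 | 28% | 18% | 7% |
| k=0.75 | 18% | 8% | 0.5% |

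Example, r=0.5: for k=1, 1 − 0.75/1.00 = 25%; for k=0.75, 1 − 0.75/0.8125 = 7.7%.

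**3. Power for a difference of 0.8** (t-test; the adjusted model loses one degree of freedom). Taking 1.6 as follow-up SD with 64 per arm:

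| Change score to adjusted | r=0.3 | r=0.5 | r=0.7 |
|---|---|---|---|
| k=1 | 66% to 84% | 80% to 90% | 95% to 98% |
| k=0.75 | 76% to 84% | 88% to 90% | 97.5% to 97.6% |

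If 1.6 is instead the SD of change, the planned 80% is met. Adjustment then gives 94%, 90% and 86% (k=1) or 87%, 83% and 80% (k=0.75) at r=0.3, 0.5 and 0.7.

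For H2 at r=0.5, with 1.6 as follow-up SD and 10% attrition:

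- Pooled controls, 195 × 0.9 ≈ 175 against 64: 93% to 98% (k=1) or 97% to 98% (k=0.75).
- Stage 2 controls only, 56 × 0.9 ≈ 50 against 64: 75% to 86% or 83% to 86%.

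**4. What a main-effect covariate does.** Let T be the arm indicator, X the covariate, g the baseline group difference and d the interaction that is tested. The planned model gives:

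- Baseline mean: a + gT + cX
- Follow-up mean: a + v + gT + dT + cX
- Difference: v + dT

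The term cX cancels. A generalised least squares fit (four visits, 64 per arm, r=0.5) confirms this: the SE of the 6-month interaction is 0.283 (k=1) or 0.255 (k=0.75) with and without the covariate, and the estimate is identical. In simulated trials with 72 per arm, a covariate explaining 25% of HbA1c variance and 10% of follow-up visits missing at random, the mean SE moved from 0.2762 to 0.2753. When the covariate also predicted change, it moved from 0.2881 to 0.2870. Both are reductions of less than 0.4%. Single estimates moved by at most 0.07.

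**5. Which imbalance remains.** Assume a true effect of −0.80 and a covariate imbalanced by 0.3 SD, which at 64 per arm has p=0.09 and so is selected.

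- If it shifts HbA1c by 0.5 per SD at every visit, the change contrast removes it: −0.80 + 0.5×0.3 − 0.5×0.3 = −0.80. Adjusting for baseline HbA1c alone gives about −0.73 (simulation, r=0.5).
- If it acts on follow-up only, the change contrast gives −0.80 + 0.5×0.3 = −0.65, with or without the main effect. Adjusting for baseline HbA1c alone also gives −0.65. Adding the covariate to a model of the follow-up value, or adding a covariate-by-visit term, restores −0.80.

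**The case against.** The strongest reply is that nothing here is invalid. The change contrast is unbiased under randomisation, 64 per arm reproduces, and if 1.6 is the SD of change the planned power is met. With the pooled controls that 4.1 describes, H2 gains only 1 to 5 points at r=0.5. All of this stands, and it limits the point to efficiency and accuracy of wording.

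Second, fixed effects need not mean main effects only: the H2 model description uses the term for a list that includes interactions. Covariate-by-visit terms are not ruled out, and they would remove imbalance in predictors of change. This stands as a reason to make the statement conditional. The only interactions listed are visit by group, however, so main effects remain the natural reading.

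Third, a reader might infer that the planned test leaves all chance imbalance in place and that baseline adjustment cures it. Step 5 of the working shows otherwise. Differencing already handles factors that act equally at all visits, and adjusting for baseline alone does not repair imbalance in a factor that predicts change.

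Fourth, a model of follow-up values only would drop patients with no follow-up visit, although the ITT set is everyone with a baseline assessment. This stands, and the fix has to meet it.

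**Conclusion.** The point holds as a matter of efficiency and clarity. H2 and H3 use a valid test that, apart from one degree of freedom, is never more precise than the baseline adjustment already chosen for Stage 1. The variance saving runs from 35% (r=0.3, k=1) to nothing (r=k). These sizes rest on assumed r and k, and the powers also on what the SD of 1.6 describes.

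The covariate finding needs no assumption about r or k. If the selected variables enter as time-constant main effects, the claimed gains in bias and power do not arise for the tested interaction with complete data, and are negligible with about 10% missing visits.

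Stronger conclusions that a reader might draw are not supported. The documents do not show that the stage 2 tests are biased by design, or that the sample size is wrong. Nor do they show that H3 tests a visit preceding its own randomisation. Its reference visit is unstated, but two features fit counting from re-randomisation at month 6: the extra calls at months 7 and 9 (M.1.2), and the restriction of distress and depression to the first two of three time points. That needs only a clarifying sentence.

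**What to change.** - For H2 and H3, name a baseline-adjusted analysis as confirmatory, as in Stage 1, with the baseline value of each outcome as a covariate.
- To keep the ITT set of all patients with a baseline assessment, a longitudinal model with equal baseline means across arms may be used for H3 (month-6 baseline) and for H2 against concurrently randomised stage 2 controls. It should not be used against pooled controls, because stage 1 usual-care patients were not randomised against the stage 2 mentees and equal baseline means are not guaranteed.
- Replace the p<0.20 screen and its power claim with a short prespecified list of prognostic covariates acting on the follow-up outcome. If baseline stays a response, enter them with covariate-by-visit terms.
- As a clarification, state that the H3 baseline is the month-6 value at re-randomisation and that H3 visits are counted from there.

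The cost is SAP wording and about one degree of freedom per covariate. Baseline and month-6 values are already scheduled in Table 1. If r is close to k, the precision gain from baseline adjustment is near zero.
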